Date: 10/18/2020 NCT04129216

*THE EFFECTS OF SHORT-TERM
PREOPERATIVE TREATMENT WITH
HORMONAL THERAPY ON GENE PROFILES
IN
BREAST CANCER*

JHM IRB - eForm A – Protocol

- Use the section headings to write the JHM IRB eForm A, inserting the appropriate material in each. If a section is not applicable, leave heading in and insert N/A.
- When submitting JHM IRB eForm A (new or revised), enter the date submitted to the field at the top of JHM IRB eForm A.

1. Abstract

- Provide no more than a one page research abstract briefly stating the problem, the research hypothesis, and the importance of the research.

Breast cancer is among the most common malignancies in women in the United States. Over the years breast cancer management have dramatically developed from the extensive surgical approach toward the breast conservative approach. This was mainly due to the introduction of chemotherapy and hormonal therapy. Hormonal therapy in particular has been shown to improve the oncological outcomes of the breast cancer. However, while this is well documented in the clinical outcomes. Little is known in regards what happens on the genetic level. As such in this study we would like to study the genetic, molecular and functional outcomes that results after a short term neoadjuvant hormonal therapy on patients with breast cancer.

The hypothesize of this study is that short-term, preoperative hormonal treatment will induce genetic changes associated with reduced proliferation, including lower Ki67 expression, and changes in ER and PR expression as well as reduced ER pathway activity. The data from such investigation will be very helpful in advancing the individualized care to women with breast cancer.

Hypothesis

- We hypothesize that short-term, preoperative hormonal treatment will induce genetic changes associated with reduced proliferation, including lower Ki67 expression, and changes in ER and PR expression. as well as changes in ER pathway activity measures

2. Objectives

The purpose of this study is to evaluate the effects of short-term preoperative treatment with hormonal therapy (tamoxifen, letrozole, and exemestane, administered according to standard of care) on gene expression profiles in patients with breast cancer. As such:

- A. Primary objective is to determine whether there is a reduction in the expression of proliferation marker Ki67, measured by IHC as well as single-gene read out, following short-term preoperative treatment with hormonal therapy.

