Secondary objectives are to determine whether short term treatment results in significant reductions in the Mammaprint risk score, or in ER or PR expression as measured by IHC and single-gene read out or a change in ER pathway activity. **C. Exploratory objectives:**

- a. Identify differentially expressed transcripts after short-term pre-operative, hormone treatment
- b. Identify transcripts for which gene expression is associate with measures of response, including changes in Ki67, ER and PR.
- c. Perform full-transcriptome set analysis to identify pathway level changes associated with treatment.
- d. Comparison of expression changes between two standard of care molecular diagnostics: 70-GS and 21-GA
- e. Perform OncoSignal pathway activity analysis on pre and post treatment samples to related pathway activity to patient response

The participants of this study will be clinical breast cancer patients of the Principal Investigator (PI) or those referred by community physicians to the PI. The breast cancer patients will be evaluated by the PI or a study team member to assess if they meet inclusion/ exclusion criteria for this study. If the patient meets all the criteria, the consent process will take place.

Participants will include 30 breast cancer patients. These patients will be recruited from Johns Hopkins University cancer treatment centers.

This is a clinical trial with three treatment groups including tamoxifen, letrozole, and exemestane. Ten pre-menopausal patients and men will be in their own group and will receive tamoxifen. Twenty post-menopausal patients will in a separate group and will receive letrozole or exemestane. Treatment selection will be at the discretion of the medical oncologist. Ten patients will be allocated to each treatment group, for a total of 30 patients.

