relevant since ER staining positive tumors are selected with an intend for hormonal treatment. From previous studies it is known that, although tumors can be ER positive in staining, the pathway is not always equally active (34). High ER pathway activity on the primary biopsy leads to a better response to hormonal therapy as compared to samples with a low ER activity on the primary biopsy, although all are ER staining positive. Also the change in pathway activity is higher in patients that respond to hormonal therapy as compared to patients that do not, or suboptimally respond, to hormonal treatment. The test requires 0.25mm³ FFPE tissue with a tumor percentage of at least 50%. In principle the same biopsy material can be used as collected for mammaprint but the processing of the FFPE samples is different

Study Drug Information(Dosage, Administration Frequency, Duration):

Tamoxifen: 20mg is administered daily. Patients take this drug for 2-6 weeks.

Letrozole: 2.5mg is administered daily. Patients take this drug for 2-6 weeks

Exemestane: 25mg is administered daily. Patients take this drug for 2-6 weeks.

b. Study duration and number of study visits required of research participants.

We anticipate this study to be done in 2 years. Following consent, and prescription of hormonal therapy, patients will have only one study visit prior to surgery, to take a baseline core research biopsy. The surgical sample will be used for post-treatment analysis

c. Blinding, including justification for blinding or not blinding the trial, if applicable.

d.

This is a single arm trial and so will not be blinded.

e. Justification of why participants will not receive routine care or will have current therapy stopped.

Participants will receive routine care. Normally, patients are scheduled for surgery after radiologic and other workups are completed. After surgery, they will receive hormonal therapy. In our study, hormonal therapy will commence after patients are recruited to the study and informed consent is signed, prior to surgery. Hormone therapy will continue after surgery.

f. Justification for inclusion of a placebo or non-treatment group.

There is no placebo or non-treatment group.

g. Definition of treatment failure or participant removal criteria.

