Treatment failure happens if the patient doesn't comply with the hormonal therapy treatment plan. At such cases, the patient will be removed from the study. If any patient miss more than two doses of the medication they will be removed from the study.

Because the duration of the study is short, and the medications are well tolerated, we expect very few non-compliant patients. We will add additional patients to the study if we lose any due to this clause.

- h. Description of what happens to participants receiving therapy when study ends or if a participant's participation in the study ends prematurely.

This is expected to be a rare event as patients are only followed for 2-6 weeks, until surgery, and the hormonal therapy administered in this study is well studied and carries minimal risk of long term effects or consequences. In such cases, patients will continue their standard of care plan as advised by their care providers.

5. Inclusion/Exclusion Criteria

A. Inclusion criteria:

- Treatment-naïve, histologically confirmed invasive ductal breast cancer between stages 1 to 3.
- Co-enrollment in the FLEX Registry
- ER+ PR+ confirmed hormone receptor status measured by immunohistochemistry(IHC)
- Patients should understand their condition and be able to give informed consent to participate

B. Exclusion Criteria:

- History of hormonal therapy, chemotherapy, radiation therapy, or novel therapy to treat the current breast cancer.
- Allergic reactions/hypersensitivity to tamoxifen, letrozole, or exemestane or any of their ingredients.
- Any contraindication to hormonal therapy, such as history of thromboembolic disease or uterine cancer.
- Patients without invasive disease (stage 0)
- Patients with metastatic breast cancer(stageIV)
- Patients that are HER2+ by IHC/FISH.

Drugs/ Substances/ Devices

a. The rationale for choosing the drug and dose or for choosing the device to be used.

The drugs in this study are FDA approved medications and drugs of choice for hormone therapy according to NCCN (National Comprehensive Cancer Network) guidelines. We will use the standard recommended daily doses of the drugs.

MammaPrint has 510k FDA clearance as a device and is a cost-effective vehicle for evaluating the genomic objectives of this study. The patient population considered for enrollment in this trial are candidates for receiving MammaPrint as a part of their standard of care.

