The rationale for using the Oncosignal in addition to Mammaprint is that Oncosignal shows differences in pre treatment ER pathway activity scores between patients, although all patients are ER staining positive this does not always relate to an active pathway. Mammaprint test can

show the gene level changes and oncosignal can show the whole pathway activity before and after treatment

- b. Justification and safety information if FDA approved drugs will be administered for non-FDA approved indications or if doses or routes of administration or participant populations are changed.**

The drugs that will be used are FDA approved to be administered for an FDA approved indication.

- c. Justification and safety information if non-FDA approved drugs without an IND will be administered.**

No non-FDA approved drugs without an IND will be administered

Study Statistics

- a. Primary outcome variable:** The primary outcome variable is Ki67 expression, a measure of tumor proliferation
- a. Secondary outcome variables:** Secondary outcomes include ER and PR expression and pathway activity patterns pre and post treatment
- b.**
- c. Statistical plan including sample size justification and interim data analysis.**

Primary Objective: Change in Ki67 expression after treatment will be calculated by subtracting %Ki67 expression at time of surgery from the baseline level. We will then fit a linear model to determine whether short-term treatment significantly reduces expression, while adjusting for choice of treatment, ER and PR level, and other possible cofounders. In a secondary analysis, we will evaluate individual treatment groups separately.

Sample size justification: Power calculations are based on the use of a one-sided, one-sample t-test to evaluate a decrease in Ki67. The proposed sample size of 30 subjects offers at least 90% power at an alpha of 0.05, to detect a decrease greater than 0.55s.d. For the analysis of individual treatment groups of 10 offer at least 90% power to detect decreases greater than 1s.d.

Secondary objectives

Determine whether short term treatment results in significant reductions in Mammaprint risk score, ER or PR expression as measured by IHC.

Change in risk score ER and PR expression will be evaluated as described above for Ki67, using linear regression to model the change in each variable while adjusting for ki67 in addition to the covariates described above. Expected power is the same as for the primary analysis.

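### The secondary regressions for MammaPrint score, ER and PR do not say what is tested, and their stated power belongs to a different, covariate-free test

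*Combined protocol and SAP*

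**What the plan says.** Under Study Statistics, item c, the primary change is the baseline value minus the value at surgery, so a positive change is a fall. It goes into a linear model "adjusting for choice of treatment, ER and PR level, and other possible cofounders". The sample size paragraph rests on a simpler test: "Power calculations are based on the use of a one-sided, one-sample t-test to evaluate a decrease in Ki67". With 30 subjects and alpha 0.05 it gives at least 90% power for a fall of 0.55 SD.

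Under Secondary objectives in the same item, MammaPrint risk score, ER and PR follow the Ki67 approach, "using linear regression to model the change in each variable while adjusting for ki67 in addition to the covariates described above". The power statement is one sentence: "Expected power is the same as for the primary analysis".

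Three other places bear on this:
- Study Procedures, item f: "There is no placebo or non-treatment group".
- The inclusion criteria require "ER+ PR+ confirmed hormone receptor status measured by immunohistochemistry(IHC".
- On direction, the Hypothesis speaks of "lower Ki67 expression, and changes in ER and PR expression", while the Objectives ask whether "short term treatment results in significant reductions in the Mammaprint risk score, or in ER or PR expression".

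No section names the coefficient or contrast to be tested, the time point of the ER, PR and Ki67 covariates, or any centring or coding.

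**The concern.** In a single-arm study, whether a marker falls is a question about its mean within-patient change. No treatment coefficient in the model answers it, because treatment enters only as the choice among three active drugs. The answer has to come from the intercept or from an adjusted mean, and the plan names neither.

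The choice matters. With ER, PR and Ki67 entered as raw levels, the ordinary intercept is the expected change in a patient whose three values are all zero. The ER+ PR+ criterion excludes such a patient, so the intercept is an extrapolation. With covariates centred at their sample means, the estimate is the mean change, but the model's standard error leaves out part of its sampling variation. In neither case is the test the one for which power was computed. Because contrast, centring and the open list of further confounders are all unsettled, they could also be chosen after the data are seen.

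**Working it through.** **Inputs from the documents.** n = 30, as three groups of 10; one-sided alpha 0.05; fall of 0.55 SD, read as the SD of the change. The named model terms are intercept, two treatment indicators, ER, PR and Ki67: 6 parameters, so 30 − 6 = 24 residual df. Covariate means, SDs and correlations are not given; those below are assumptions.

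**1. The plan's own figure.** Noncentrality is 0.55 × √30 = 3.012 and the critical value is t(0.95; 29) = 1.699. Power = 1 − F(1.699; 29 df, 3.012) = **90.3%**. The stated 90% reproduces.

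**2. Adjusted mean change, centred covariates that explain nothing.** The noncentrality is the same, with 24 df and critical value 1.711. Power = **90.0%**. The lost degrees of freedom cost about 0.3 points.

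**3. Ordinary intercept, uncentred covariates, treatment coded to average over groups.** Let m be each covariate's mean in units of its own SD. In units of the residual variance,

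var(intercept) ≈ 1/30 + Σm²/29.

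At m = 1/1/1 this is 0.0333 + 3/29 = 0.1368. The SE is 0.370, the noncentrality 0.55/0.370 = 1.487, and power 42%. The formula ignores chance correlation of the covariates with each other and with treatment group. Simulation with independent normal covariates unrelated to the change includes it and gives somewhat lower values:

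| Assumed m (ER/PR/Ki67) | Formula | Simulation |
|---|---|---|
| 0.5/0.5/0.5 | 71% | 66% |
| 1/1/1 | 42% | 38% |
| 2/1.5/1 | 26% | 23–24% |

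**4. Type I error of the centred model.** With equal groups and covariates centred at the sample mean, the adjusted mean averaged over groups is simply the sample mean change. Its variance as an estimate of the population mean change is σ²/30. If the covariates explain a fraction R² of the variance of the change, the model reports about σ²(1 − R²)/30, because it treats the sample covariate means as fixed. The type I error is therefore P(T₂₄ > 1.711 × √(1 − R²)):

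| R² | Effective cut-off | Formula | Simulation of this model | Paired t-test |
|---|---|---|---|---|
| 10% | 1.623 | 5.9% | 5.6–5.9% | about 5% |
| 25% | 1.482 | 7.6% | 7.4–7.5% | about 5% |
| 50% | 1.210 | 11.9% | 11.7–11.8% | about 5% |

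Such R² values are not far-fetched. Read literally, the carried-over covariates put ER level in the model for ER change and PR level in the model for PR change. If baseline and surgical values have equal variance and correlation ρ, the squared correlation of the change with baseline is (1 − ρ)²/[2(1 − ρ)] = (1 − ρ)/2. That is 10%, 25% and 50% at ρ = 0.8, 0.5 and 0.

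**5. Sidedness.** A two-sided 0.05 paired t-test at 0.55 SD has 83% power and needs 0.61 SD for 90%.

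**The case against.** The plan nowhere says that the raw intercept is tested. It asks whether treatment lowers each marker, refers back to the Ki67 approach, and bases power on a one-sample t-test; all three point to the mean change. On that reading the power is 90.0% to 90.3% and the power sentence is right. This stands. A reader might infer from step 3 that the secondary endpoints are underpowered, or that a real fall of the planned size would go undetected. The documents do not support that: it needs a test the plan never states and covariate means it never gives, and the result ranges from 66% down to 23% as those assumptions change.

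The charitable reading does not settle the matter, however. If the adjusted mean is tested, power is kept, but step 4 shows that the standard error is too small for the population mean change.

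On sidedness, the Objectives and the statistical section both ask about reductions, and the borrowed power is one-sided. Only the Hypothesis, which speaks of changes in ER and PR, is out of line. This is a minor wording matter.

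**Conclusion.** The point holds as a gap in specification and a mismatch between the described model and the test behind its power figure. The 90% is not an arithmetic error: it belongs to the t-test of the mean change. It does not carry over to the ordinary intercept with uncentred covariates; the powers shown for that case are illustrations on assumed covariate means. The adjusted mean with sample-centred covariates keeps power, at the price of a one-sided type I error of about 5.6–5.9%, 7.4–7.6% and 11.7–11.9% where covariates explain 10%, 25% and 50% of the variance. These figures depend on the assumed R², on equal groups of 10 and on normal errors. The primary Ki67 model has the same unnamed contrast, so both should be corrected together. The omission is certain from the text; its numerical effect depends on choices the plan has not made.

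**What to change.** State in Study Statistics, item c, that the main test for each of MammaPrint score, ER and PR, and for primary Ki67, is a one-sided one-sample (paired) t-test of the mean change at alpha 0.05. The power sentence can then say that 30 evaluable pairs give about 90% power for a mean fall of 0.55 SD of the change, and that figure will apply to the test performed.

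Keep the regression as a supporting analysis of how the change varies with treatment and with baseline ER, PR and Ki67. Use baseline values only, centred, name any further confounders in advance, and leave Ki67 change out as a covariate.

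Align the Hypothesis with the Objectives on direction for ER and PR. If a two-sided test is wanted there, quote 83% at 0.55 SD, or 90% at 0.61 SD.

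The cost is a few sentences, with no added patients or assays. The one small downside is that the unadjusted test forgoes the apparent power gain from covariates (about 91.5% and 93.5% instead of 90.3% when they explain 10% and 25%), but that gain comes with the inflated type I error in step 4.

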Exploratory analyses

Identify differentially expressed transcripts after short-term pre-operative, hormone treatment

Identify transcripts for which gene expression is associate with measures of response, including changes in Ki67, ER and PR expression.

We will fit empirical Bayes linear models [32] to identify genes for which expression is associated with response to treatment, controlling type I error at an FDR of <10%. Wilcoxon Rank Sum tests will be used to perform Gene set enrichment analysis on the results to identify pathways that are significantly altered after short-term treatment. [33]

Show differences in pre treatment ER pathway activity scores between patients, although all patients are ER staining positive this does not always relate to an active pathway. Show differences in ER pathway activity scores between pre and post treatment samples, indicating a measurable biological effect of the treatment.

d. Early stopping rules.

There are no early stopping rules.

6. Risks

a. Medical risks, listing all procedures, their major and minor risks and expected frequency.

Important drug adverse effects like increased risk of thromboembolism would be considered a major risk. The other non-specific side effects may be considered as minor risk. Since the drugs are administered over a short period, it is highly unlikely to develop an adverse event that requires chronic use of the drug.

The Oncosignal test has minimal risks:

It is noninvasive, does not require an invasive sampling that presents significant risk, does not introduce energy into a subject and is not used as a diagnostic procedure without confirmation of the diagnosis by another medically established diagnostic product or test

The Oncosignal results will not be shared with patients(subjects), treating physicians; nor will be used for patients' management; It only will be used for research purposes.

b. Steps taken to minimize the risks.

Known adverse effects of tamoxifen and anastrozole will be recorded using a checklist every week by the research assistant. Medical monitoring will be made by both the principle investigator and the Institutional Data and Safety Monitoring Board. Patients are informed about all common and important adverse effects and they are advised to report as soon as they notice them. They are also advised to take some preventive measures for example for the prevention of

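### The only gene-level model is worded as association with response, but its results are read as pathways altered by treatment; no before/after transcriptome model is stated

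*Combined protocol and SAP*

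**What the plan says.** Section 2 gives the purpose of the study as the effect of preoperative hormonal therapy "on gene expression profiles in patients with breast cancer". Under Exploratory objectives it separates three aims:

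- Objective a asks which genes change once patients have been treated: "Identify differentially expressed transcripts after short-term pre-operative, hormone treatment".
- Objective b asks a different question, namely which transcripts go with how far a patient's Ki67, ER and PR moved.
- Objective c is set at pathway level: "Perform full-transcriptome set analysis to identify pathway level changes associated with treatment".

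Under Study Statistics, Exploratory analyses, the headings for a and b are repeated, and one methods paragraph follows. Its gene-level sentence begins "We will fit empirical Bayes linear models [32] to identify genes for which expression is associated with response to treatment", with the FDR held below 10%. Its second sentence applies Wilcoxon rank-sum tests to "perform Gene set enrichment analysis on the results to identify pathways that are significantly altered after short-term treatment".

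The end of Section 2 and Section 4a also say that the biopsy and surgical profiles will be compared. Neither names a contrast, a pairing or a test. The closing lines of the Exploratory analyses mention differences before and after treatment, but in ER pathway activity scores (the OncoSignal assay), not in the transcriptome.

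**The concern.** The average change in a gene after treatment and the association of that gene with response are different parameters. A pathway that falls by a similar amount whether or not the patient responds has a large average change and no association. A pathway that rises in some patients and falls in others, in step with Ki67, has a strong association and no average change. If enrichment is run on the association results and reported as alteration by treatment, the first pathway can be missed and the second reported under a label it has not earned.

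The text also leaves open whether the expression entering the response model is the baseline value or the change. If it is the baseline value, the ranking uses no post-treatment expression at all, and the label fits even less well. Two analysts working from this paragraph could report different pathways under the same description.

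**Working it through.** **The plan's own figures.** No power or sample size is given for the transcriptome analyses. The stated power figures concern Ki67. With a one-sided one-sample t-test at 0.05, noncentral-t power is 90.25% for n = 30 at 0.55 s.d. and 89.75% for n = 10 at 1 s.d., against a stated 90%. They reproduce and have no bearing on this point.

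**Objectives against methods.**

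| Objective | Quantity needed | Method stated |
|---|---|---|
| a | mean change, surgery minus baseline, per transcript | none, read literally |
| b | association with change in Ki67, ER, PR | empirical Bayes model, FDR below 10% |
| c | pathway-level change with treatment | rank-sum enrichment on the results of b |

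**How far apart the two rankings are.** From the protocol: 30 patients, each with a pair of samples. Assumed: 5,000 genes, a set of 50, unit s.d. of change, ordinary rather than moderated t, expression entering as change, two-sided 5% rank-sum test, 300 trials per setting. For a gene with mean shift d (in s.d.) and correlation r with response:

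- Paired t is centred near d × √30. For d = 0.3, 0.5 and 0.8 this gives 1.64, 2.74 and 4.38.
- Association t is centred near r × √28 / √(1 − r²). For r = 0, 0.05, 0.1 and 0.4 this gives 0, 0.26, 0.53 and 2.31. The shift d does not appear, because the intercept absorbs it.

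| Set of 50 genes | Flagged, response ranking | Flagged, paired ranking |
|---|---|---|
| shift 0.3 to 0.8, r = 0 | about 5% | 100% |
| shift 0.5, r = 0.05 | about 46% | 100% |
| shift 0.5, r = 0.1 | about 92% | 100% |
| shift 0, r = 0.4 | 100% | about 54% |

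Repeat runs gave 3% to 8% in the first row, 43% to 49% in the second, 92% to 94% in the third and 52% to 54% in the last. Monte Carlo error at 300 trials is up to √(0.5 × 0.5 / 300) = 2.9 points.

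**Why the paired ranking still flags the last set.** Fifty genes each correlated 0.4 with one response are correlated 0.4 × 0.4 = 0.16 with each other, so their t values move together. The s.d. of the set's mean t is about √(0.16 + 0.84/50) = 0.42. The rank-sum test assumes about 1/√50 = 0.14, so its cut-off is near 1.96 × 0.14 = 0.28. A normal variable with s.d. 0.42 exceeds 0.28 in size about 51% of the time, in line with the simulation. A rate near 3% appears only if the simulated response is forced to average exactly zero in every trial.

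**The case against.** The strongest reply is that the paragraph is loose rather than wrong. Both headings stand above it, it speaks of models in the plural, and response to treatment could mean transcriptional response, which would make the pathway sentence consistent. Section 2 and Section 4a commit to comparing the two samples. The primary analysis already works with within-patient change in Ki67, and the secondary analyses carry that to the risk score, ER and PR. This stands as evidence of intent. It does not supply a model. The heading immediately above the paragraph describes response through changes in Ki67, ER and PR, so the natural reading of the next line is objective b.

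A second reply is that the near-chance detection rate needs a change wholly unrelated to response, and a correlation of 0.1 removes most of the loss. Section 4, in its description of OncoSignal, expects the change in ER pathway activity to be larger in responders. This stands too. A reader might infer that the drug effects most expected would be missed; the documents do not support that, at least for the ER pathway.

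A reader might also infer that the plan cannot deliver objectives a and c. That goes too far: paired samples are collected, and the cited empirical Bayes framework can fit a paired contrast.

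**Conclusion.** The point holds as a fault of specification and labelling. Followed as written, the plan gives no test for objective a and answers objective c with the ranking for objective b. Under the assumed settings, the cost for a pathway that changes independently of response is detection at about 5% instead of 100%, shrinking quickly once the change tracks response. In the other direction, a pathway with no average change but correlation 0.4 with response is called altered in 100% of trials. Switching to the paired ranking lowers this only to about 54%, so it should not be presented as a full cure. The remainder comes from the rank-sum test ignoring inter-gene correlation, which is a separate weakness.

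The rates depend on assumed gene numbers, set size and correlations, none of which the protocol gives. The distinction between the two quantities does not depend on them. These analyses are exploratory, and the Ki67 conclusion and the secondary analyses are untouched. The change should be made, but the trial's main result does not hang on it.

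**What to change.** In Study Statistics, Exploratory analyses, replace the single model sentence with two.

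1. For objectives a and c: an empirical Bayes linear model of the within-patient change in log expression (surgery minus baseline), testing for zero mean change with FDR below 10%. The moderated t from this model ranks the genes for the pathway test. How the three treatment groups enter should be stated; weighting them equally is optional.
2. For objective b: a separate model of association with change in Ki67, ER and PR, stating whether expression enters as baseline or as change. Any pathway found from this model is reported as associated with response, not as altered after treatment.

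The wording should be settled before the paired expression results are examined, so that the choice of ranking cannot follow the data. The cost is a few lines of text and one extra model fit on data already collected, with no added patients or samples.
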